12.0 PHARMACOVIGILANCE

12.1 Definitions

Adverse Event (AE) - An adverse event is any untoward medical occurrence in a patient from trial-specific procedures. An AE may therefore be any unfavourable and unintended sign (including abnormal findings), symptom or disease concurrently associated with the use of the trial procedures.

Adverse Events of Medical Significance:

1.Adverse Reaction (AR) - An adverse reaction is any untoward and unintended response in a patient to a trial procedure which is related to any dose (e.g. radiotracers) administered to that patient. Note: Any adverse event judged by either the reporting investigator or the sponsor as having reasonable causal relationship to the trial procedures qualifies as an AR if there is evidence or argument to suggest a causal relationship.

2.Serious Adverse Event / Reaction (SAE / SAR) - A serious adverse event or reaction in a trial subject that:

- results in death,
- is life-threatening,
- requires in-patient hospitalisation or prolongation of existing hospitalisation,
- results in persistent or significant disability / incapacity
- is a congenital anomaly / birth defect, or
- other important medical condition (medical judgement should be exercised in deciding whether an adverse event / reaction should be classified as serious in other situations. Important adverse events / reactions that are not immediately life-threatening or do not result in death or hospitalisation, but may jeopardise the subject or may require intervention to prevent one of the other outcomes listed in the definition above, should also be considered serious).

Note: For the purpose of this definition, life-threatening refers to an event in which the trial patient was at risk at the time of an event; not an event that might have caused death if it were more severe.

Events not to be treated as SAEs: The following events do not require reporting as an SAE, but must be recorded in the relevant section(s) of the CRF

- Disease related illness / events
- Elective hospitalisation
- Disease related deaths

12.2 Detecting and reporting AEs

All adverse events relating to the study procedures that occur between informed consent and end of trial procedures must be recorded in the patient notes. If the patient is at the WMIC then the clinical fellow or another appropriately trained member of the team must ensure that the event is recorded using the protocol at WMIC and the information is also recorded in the patient notes (which will be held at the research hospital). Every effort should be made to maintain a complete record of adverse events.

Where required, adverse events will be reported to MAHSC CTU via completion on the trial CRF. Serious adverse events should also be reported immediately on an SAE report form, as detailed in section 12.2.1 below.

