4.3.1 Withdrawal of patients

When consenting to the trial, patients are consenting to trial procedure, trial follow-up and data collection. Patients will be withdrawn from scanning prior to completion for the following reasons:

- Adverse event or an intercurrent illness
- Unable to complete the visits or study documentation (such as questionnaires etc) as required
- Deterioration in health
- Patient decision
- Investigator decision
- For safety reasons e.g. recommendation of IDMC that trial should not continue.
- Benzodiazepines and other drugs known to influence microglial activation, e.g. minocycline or corticosteroids in the last three days prior to the PET scan
- If a patient is withdrawn from the PET scanning prior to having a tracer there is no need to complete the follow-up.

Patients will only be withdrawn from further follow-up in the case of:

• Patient explicitly stating their wish not to contribute further data to the study

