9.0 TRIAL ASSESSMENTS

PHASE 1

Table 1. Schedule of assessment for phases 1 and 2.

		Trial Procedure (ARM A)		Trial Procedure (ARM B)		3 months after stroke**
	Screening Assessment*	Visit 1	Visit 2	Visit 1	Visit 2	
		Assessm	ents			
National Institutes of Health Stroke Scale (NIHSS)	Х					X
Modified Rankin Scale (mRS)	Х					х
Tolerability questionnaire			Х	Х		
Adverse Event Log		Х	Х	Х	Х	Х
Concomitant/Prohibited Medications	Х	x	Х	Х	х	
		Tests	5			
Blood tests***		х		х		
MRI scan (with and without contrast) ⁺		X+	X+	X+	X+	
PET scan ([¹¹ C]-(R)- PK11195)		X			х	
PET scan ([¹⁸ F]GE- 180) ****			х	Х		

* Carried out whilst patient is still in hospital ** Carried out at the hospital site *** Whole blood sample (3ml EDTA tube) and plasma sample (2ml cryovial) **** Two blood samples of 10ml each may be taken per scan for the measurement of radioactivity.

⁺ To be carried out on either Day 1 or Day 2.

PHASE 2

	Screening Assessment*	Trial Procedure	3 months after stroke**		
	Assessi	ments			
National Institutes of Health Stroke Scale (NIHSS)	Х		Х		
Modified Rankin Scale (mRS)	Х		Х		
Adverse Event Log		Х	Х		
Concomitant/Prohibited Medications	Х	Х			
Tests					
Blood tests***		Х			
MRI scan (with and without contrast)		х			
PET scan ([¹⁸ F]GE- 180)****		Х			

* Carried out whilst patient is still in hospital

** Carried out at the hospital site

*** Whole blood sample (3ml EDTA tube) and plasma sample (2ml cryovial)

**** Two blood samples of 10ml each may be taken per scan for the measurement of radioactivity.

Two weeks after initial stroke, most patients would expect to switch tablets from aspirin to clopidogrel as a national recommendation. At each scan visit, a vein will be cannulated for the scanning procedure. Venous access is needed for the administration of the contrast agent in Magnetic Resonance Imaging (MRI) and of the radiopharmaceutical in Positron Emission Tomography (PET). The cannula can be removed on completion of the visit that day. If possible, blood will be taken from the administration cannula at the time of insertion. This can be sometimes difficult and may necessitate a further venepuncture for another blood sampling cannula.

Three types of blood analysis may be performed.

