12.2.1 SAE Processing and Reporting at the MAHSC-CTU

AEs meeting the definition of a Serious Adverse Event (SAE) must be reported to the MAHSC-CTU using the trial specific SAE Report Form **immediately**, and within 24 hours of observing or learning about the event.

Centres should respond as soon as possible to requests from the CI or designated representative (via the MAHSC-CTU) for further information that may be required for final assessment of the SAE.

All SAEs must be reported by faxing a completed SAE Report Form **immediately**, **and within 24 hours** of becoming aware of the event to the IN_CVD Trial Manager at the MAHSC-CTU

[contact]

On receipt of the SAE Report Form, the CTPM will send an acknowledgement of the SAE to the relevant members of the trial team at the participating site. This acknowledgement will include an SAE reference number which should be included on all future correspondence regarding the SAE. The CTPM then passes the SAE form to the CI. The CI reviews the site PI's assessments of seriousness and causality.

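### Sections 12.1 and 12.2 confine adverse events to those tied to study procedures, up to an undefined end point, which conflicts with the later causality review and, on the natural reading, with the 3-month log in Table 1

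*Protocol*

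**What the plan says.** - **Definition (Protocol 12.1).** "An adverse event is any untoward medical occurrence in a patient from trial-specific procedures". The next sentence is looser and speaks of signs, symptoms or disease associated in time with use of the procedures. An adverse reaction is defined separately, by a causal link to an administered dose.
- **Recording rule (12.2).** The duty covers "All adverse events relating to the study procedures that occur" "between informed consent and end of trial procedures must be recorded in the patient notes". The protocol does not say when trial procedures end.
- **Schedule (9.0, Table 1).** In both phases the row "Adverse Event Log" is marked at each scan visit and again under "3 months after stroke". Scan visits sit under a trial-procedure heading and follow-up has its own column.
- **Consent (4.3.1).** Procedure and follow-up are listed as different things: "patients are consenting to trial procedure, trial follow-up and data collection".
- **Causality (12.2.1 and 12.2.2).** The chief investigator reviews the site's "assessments of seriousness and causality" once a serious event has been reported. Causality and expectedness are then evaluated for expedited reporting.
- **Tracer status (8.1).** GE-180 is unregistered, its safety profile is still being investigated, and side effects not yet documented may occur.

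**The concern.** Section 12 contains two different ideas of what an adverse event is. In one, the site must link the event to a procedure before it counts. In the other, events are collected and their cause is judged later by people other than the reporting site. Under the first, the second has less to work on: the chief investigator, the sponsor and the IDMC can assess only what was recorded.

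This matters more for a new tracer than for an established one. An effect that nobody has described is the kind a site is least able to attribute when it sees it. If attribution is the condition for recording, such an effect could be filtered out before anyone can see a pattern across patients.

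The end point in 12.2 adds a second difficulty. If trial procedures end with the last scan, the recording duty in 12.2 stops before the 3-month visit at which Table 1 still asks for a log.

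**Working it through.** The protocol gives no figure to reproduce, so the check sets the passages side by side.

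**Step 1: is attribution needed before an event counts?** The 12.1 definition uses *from* and 12.2 uses *relating to*. Read plainly, both require a link to a procedure. The second sentence of the 12.1 definition could be read as association in time only, so 12.1 is ambiguous. The recording sentence in 12.2 has no such qualifier.

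**Step 2: does the rest of section 12 fit that reading?**

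| Place | What it presupposes |
|---|---|
| 12.1, note on adverse reactions | An adverse event becomes a reaction if the investigator or the sponsor judges it causally related. The step does little if relatedness was already required, and the sponsor cannot judge an event that was never recorded. |
| 12.1, events exempt from SAE reporting | Disease-related events and deaths are exempted. If only procedure-caused events were adverse events, these would need no exemption. |
| 12.2.1 | The chief investigator reviews causality after the report arrives. |
| 12.2.2 | Causality and expectedness are evaluated after the report arrives. |

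All four fit a definition that is neutral as to cause. None fits well with the wording in 12.1 and 12.2.

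**Step 3: does the serious-event rule escape the filter?** No. Section 12.2.1 applies to adverse events that meet the seriousness definition, so it takes over the scope of *adverse event* from 12.1. The same holds for the call in 12.2 for a complete record.

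**Step 4: does the time limit conflict with Table 1?** Table 1 separates the procedure columns from the 3-month column, and 4.3.1 separates procedure from follow-up. On that usage the window in 12.2 closes at the last scan visit, while Table 1 logs events at 3 months. The term is undefined, however, so this is the natural reading and not the only one.

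**Step 5: does the 3-month log solve the attribution problem?** It solves timing, not scope. The log holds adverse events as the protocol defines them, so a site applying 12.1 strictly could leave an unattributed event out of it.

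**Step 6: what is left uncovered?** Disease-related events go in the CRF (12.1), deaths are analysed as an outcome (11.4), and symptoms of recurrent stroke are assessed at 3 months (9.0). What remains is chiefly the event that is neither disease-related nor attributed by the site to a procedure.

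**The case against.** The strongest case for the current text has four parts.

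1. **The end point may include follow-up.** The Trial Summary names the 3-month follow-up and then says that all other procedures take place elsewhere, which can be read as counting follow-up among the procedures. On that reading 12.2 and Table 1 agree. This stands: the timing conflict rests on the natural reading only. It leaves the attribution limit untouched.
2. **Both passages can be obeyed.** The sentence in 12.2 concerns the patient notes, while Table 1 separately requires a log at 3 months, and 15.2 allows no deviation except as an urgent safety measure. A reader might infer that events after the scan need not be recorded at all. The protocol as a whole does not support that, because a site following Table 1 completes the log.
3. **Other safeguards exist.** SAE reporting in 12.2.1 has no end date, 12.5 foresees a SUSAR after a patient has left the trial, and the IDMC reviews accruing trial data (13.1.2). A reader might infer that unattributed events never reach review. That is too strong; they may not reach it. But 12.5 sets no recording duty, and the SAE rule inherits the filter.
4. **The gap has no known length.** A reader might put a number of days on the period between the last scan and the 3-month visit. The readable text gives no scan day, and the timeline figure is not shown. The 4-week limit in 5.3 applies to the screening clinical assessments, not to the scan. Any figure would be an assumption about the scan day, and would also presuppose the contested reading in the first part.

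It can also be said that collecting events of any cause is a choice of scope. That is fair in general, but this protocol's own causality steps already assume it.

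**Conclusion.** The inconsistency is real and should be corrected. Its firm part is the attribution filter in 12.1 and 12.2, which conflicts with the note on adverse reactions, the disease-related exemptions and sections 12.2.1 and 12.2.2. It holds however the end of trial procedures is read. The time conflict with Table 1 is secondary and depends on reading procedures as excluding follow-up, which Table 1 and 4.3.1 support but the protocol does not define.

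The consequence is a possible loss confined mainly to events that are neither disease-related nor attributed to a procedure. For serious events the effect depends on how strictly a site reads 12.1. Neither the number of events at risk nor the length of the gap can be estimated from the document. The point bears on the completeness of safety data for an unregistered tracer. It does not touch the outcome analysis.

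**What to change.** Reconcile the passages with two wording changes:

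- **12.1:** define an adverse event irrespective of cause, and keep *adverse reaction* for events with a suspected causal link. Leave the list of disease-related exemptions from SAE reporting unchanged.
- **12.2:** remove the restriction to procedure-related events, and state that recording runs from informed consent to the 3-month visit. The start is the one 12.2 already gives, and the end is the one Table 1 already schedules.

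Sections 12.2.1 and 12.2.2 then work as written.

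The cost is a protocol amendment and somewhat more event recording for the planned 50 patients, because both the definition and the stated window become wider. No visit is added: the 3-month assessment and its log are already in Table 1.

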12.2.1 SAE Processing and Reporting at the MAHSC-CTU

AEs meeting the definition of a Serious Adverse Event (SAE) must be reported to the MAHSC-CTU using the trial specific SAE Report Form **immediately**, and within 24 hours of observing or learning about the event.

Centres should respond as soon as possible to requests from the CI or designated representative (via the MAHSC-CTU) for further information that may be required for final assessment of the SAE.

All SAEs must be reported by faxing a completed SAE Report Form **immediately**, **and within 24 hours** of becoming aware of the event to the IN_CVD Trial Manager at the MAHSC-CTU

[contact]

On receipt of the SAE Report Form, the CTPM will send an acknowledgement of the SAE to the relevant members of the trial team at the participating site. This acknowledgement will include an SAE reference number which should be included on all future correspondence regarding the SAE. The CTPM then passes the SAE form to the CI. The CI reviews the site PI's assessments of seriousness and causality.

12.2.2 Detecting and reporting a SUSAR

If an SAE is suspected to be a SUSAR, regulatory time constraints apply for expedited reporting. The CTPM will then liaise with the CI to evaluate the event for seriousness, causality and expectedness to determine whether or not the case qualifies for expedited reporting.

[figure not shown]

Figure 3. Flow diagram to describe the reporting procedure for adverse events/reactions.

SAEs assessed as having a causal relationship to the radiotracer and as being unexpected (SUSARs) will undergo expedited reporting to the relevant authorities and GE Healthcare by the MAHSC-CTU.

12.3 Pregnancy Reporting

All patients will be asked to complete a pregnancy questionnaire prior to scanning, as per standard local procedures (following SOPs at WMIC). However, if a patient becomes pregnant during the trial, the patient must be withdrawn from study immediately. The pregnancy of a patient must be reported to the MAHSC-CTU using the Pregnancy Notification and Outcome Form immediately, and within 24 hours of the participating site becoming aware of the pregnancy. The PI must obtain consent to follow the pregnancy and liaises with the obstetrician until delivery/outcome and for the postpartum period. Parental and neonatal outcomes must be recorded (by updating the Pregnancy Notification and Outcome form) even if they are completely normal and without AEs. Abnormal outcomes for the foetus or child observed at birth or during the follow-up period (e.g. spontaneous or therapeutic abortion, stillbirth, neonatal death, congenital abnormality) are considered SAEs and are reported to the MAHSC-CTU on the trial specific SAE form.

The MAHSC-CTU will fax all Pregnancy Reports to the sponsor immediately, but within 24 hours of the MAHSC-CTU becoming aware.

12.4 New Safety Findings

If a new safety finding emerges (from sources such as IMP manufacturers, data analysis, IDMC findings), the CI will review the finding for its impact on the patients participating in the relevant trial(s). If there is a potential impact on patient's safety, the sponsor will take appropriate action in conjunction with the CTPM, CI and research team. Appropriate reporting mechanisms will be followed in the event of actions being taken.

12.5 Urgent Safety Measures

Where an urgent safety measure (to prevent immediate hazard to patient's health and safety) is necessary, prior authorisations from the MHRA and ethics are not required.

If the PI takes urgent action that is not consistent with the protocol to prevent harm to a patient on a trial, the PI must immediately inform the CI and CTPM and give full details of the measures taken and the decision making process surrounding the action(s) taken. The CTPM will inform the CI, sponsor, ethics and the MHRA of these measures immediately, but no later than 3 days of the actions being taken.

An amendment will be formally submitted as soon as possible by the CI and CTPM to the relevant bodies in conjunction with the sponsor.

Examples of issues requiring urgent safety measures may be:

- A single report of a SAR with an unexpected outcome (e.g. death)
- An increase in rate of occurrence of SAR which is judged to be clinically important
- A post-trial SUSAR occurring after the patient has left the trial
- A new event relating to the use or development of the IMP likely to affect the safety of patients e.g.:
 - an SAE that could be associated with the procedures and which could lead to modification of the trial conduct

12.6 Periodic Safety Reports

Annual progress reports will be submitted to the REC, in accordance with their procedures.

A Development Safety Update Report (DSUR) will be submitted annually to the MHRA and REC in accordance with requirements.

These periodic reports will be prepared by MAHSC CTU with the input and review of the chief investigator and will be circulated to the sponsor and participating sites.

13.0 TRIAL MANAGEMENT AND OVERSIGHT ARRANGEMENTS

13.1 Oversight Committees

13.1.1 Trial Management Group (TMG)

A Trial Management Group (TMG) will be established and will include those individuals responsible for the day-to-day management of the trial.

Notwithstanding the legal obligations of the Sponsor and Chief Investigator, the TMG have operational responsibility for the conduct of the trial including monitoring overall progress to ensure the protocol is adhered to and to take appropriate action to safeguard the patients and the quality of the trial.

The TMG will meet at least quarterly once the trial is actively recruiting. Minutes will be taken at TMG meetings and copies of the minutes will be filed in the Trial Master File. The CTPM and CI will ensure that all relevant issues and actions discussed during the meeting are followed up and resolved and details of significant issues will be made available to participating sites. Minutes of all TMG meetings are available on request.

13.1.2 Independent Data Monitoring Committee (IDMC)

An IDMC will be instigated to review accruing trial data and to assess whether there are any safety issues that should be brought to the patient's attention, whether any safety amendments should be made or if there are any reasons the trial should not continue. The IDMC will conduct an early safety review after the first 10 patients. The IDMC will provide a recommendation for the trial by month 12 (end of phase 1).

The IDMC will be independent of the investigators, funder and sponsor. The CI and TMG with the support of the MAHSC-CTU will be responsible for nominating IDMC members. The Committee's terms of reference, roles and responsibilities will be defined in a charter agreed by all members of the IDMC. This charter will outline any stopping rules and the frequency of analysis and IDMC meetings during the trial. The IDMC will meet in confidence at regular intervals, as appropriate to the progress of the trial and as per the schedule agreed with IDMC members.

Reports to the IDMC will be prepared and presented by the trial team and CTPM prior to the IDMC meeting. The IDMC Chairman will then report their recommendations to the Chairman of the TMG and may request additional reports or information if required. This report will be submitted to the TMG, and if required, the REC and the MHRA and the CI and CTPM will ensure that all actions and recommendations are followed up.

13.2 Trial management: MAHSC-CTU

13.2.1 Data Collection

Each research site is responsible for maintaining source data for their trial patients in their medical notes, and for transcribing this data onto a trial specific case report form (CRF). All entries on the CRF, including corrections, must be made by an authorised member of trial staff. Research site staff will also provide trial patients with copies of the tolerability questionnaire at the time indicated on the schedule of assessments.

Research sites will submit original completed copies of the CRF and patient completed questionnaires to MAHSC CTU, keeping a copy at site with the Investigator Site File. The hospital sites and WMIC will each have site files, there will be a CRFs which must be completed and filed at the hospital sites.

13.2.2 Data Handling at MAHSC-CTU

Data provided to the MAHSC-CTU will be checked for errors, inconsistencies and omissions. If missing or questionable data are identified, the MAHSC-CTU will request that the data be

clarified. All aspects of data collection and handling throughout the life cycle of the trial will be described in trial specific documents held in the trial master file at MAHSC CTU.

Upon completion of relevant data management processes prior to any interim/ final analysis the trial data will be passed to the trial statistician for analysis.

All data handling and analysis will be conducted in line with Good Clinical Practice guidelines and the Data Protection Act 1998.

